6. SPECIFIC AIMS

Aim 1. To examine the feasibility of combining ACT with two different varenicline-assisted quitting strategies: a) slower titration of lower dose varenicline, versus b) standard titration of standard dose varenicline - - both

delivered using a flexible quit date paradigm that allows gradual preloading of varenicline prior to the target quit date (TQD).

Hypothesis 1A. There will be high demand from SMI smokers to participate in the trial as evidenced by achieving targeted accrual rates and budgeted recruitment costs.

Hypothesis 1B. Combining ACT with both dosing strategies will be practical as evidenced by high rates of study and ACT counseling session retention, and completion of study procedures.

Hypothesis 1C. Acceptability of the flexible quit date and varenicline dosing strategies will be high as demonstrated by good adherence to making a quit attempt within the quit window and taking at least 80% of prescribed study medication doses. Satisfaction with ACT either delivered in person or via telephone will be high consistent with our prior work in bipolar smokers.

Aim 2. To explore whether nicotine clearance rate as measured by the plasma 3'-hydroxycotinine / cotinine NMR influences the incidence of NPSAEs and medication tolerability in varenicline-treated SMI smokers.

Hypothesis 2. We hypothesize that slow nicotine metabolisers will exhibit trends for more neuropsychiatric adverse events (NPSAEs) of any severity to standard varenicline dosing compared with normal metabolisers treated with low dose varenicline.

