Over the past two decades there have been improved efforts to address this neglected epidemic in harder-to-treat SMI smokers (1); however, in general, advancements in cessation treatment research among SMI smokers far lags that of NMI smokers. Additionally, exciting new research results such as 1) how genetically informed biomarkers of nicotine clearance moderate smoking cessation medication treatment outcomes (7), 2) varenicline preloading increases smoking cessation rates (8), and 3) novel behavioral interventions such as ACT therapy can boost quit rates (9,10), have not been adequately tested in SMI smokers. Thus, the purpose of this proposal is to test the feasibility of whether these treatment innovations can be applied in SMI smokers with high rates of demand, practicality and acceptability for subsequent use in a large randomized clinical trial (RCT).

How Does an SMI Smoker's NMR Affect Treatment Response and Adverse Event Propensity? The NMR as measured by the ratio of 3'-hydroxycotinine (the breakdown product of cotinine) divided by the

concentration of cotinine (the breakdown product of nicotine) in a smoker's blood or urine is a genetically-informed biomarker of nicotine clearance (7). It is a surrogate measure of CYP2A6 activity - - the liver enzyme that catabolizes nicotine and other drugs and which is under genetic control11. Studies in NMI smokers have found that classifying smokers into slow versus normal nicotine metabolisers based on a cutoff score for this ratio affects how that individual is likely to respond to the 1st-line smoking cessation medications both in terms of treatment efficacy and propensity to develop side effects (7,12). The NMR predicts treatment responses to varenicline delivered at standard doses: among slow metabolisers, which represents ~40% of the general population of NMI smokers, varenicline users had comparable quit rates to nicotine patch-treated smokers and were more vulnerable to side effects than normal metabolisers. However, varenicline standard dose treatment produced higher quit rates than patch in normal metabolisers (7). To our knowledge, the NMR ratio has not been examined in a RCT of varenicline in SMI smokers. This gap is important to fill given that varenicline is the most effective monotherapy treatment for SMI smokers and these individuals have a greater propensity to develop NPSAEs.

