9. RESEARCH DESIGN AND METHODS

Overview: This pilot trial is a Phase IV, 12-week, single center, randomized, double blind, parallel group comparison of low (0.5 mg twice daily with slower titration over one full week) versus standard dose (1.0 mg twice daily with standard titration) varenicline in SMI individuals with DSM-V BD or SSD with a 12-week, post-treatment follow-up (see Figure 3 for study design). The 16 visits after screening (Weeks 0-24) will take place using the guidelines developed by the UCSD Office of the Vice Chancellor for Research. Participants will be screened, randomized and follow the protocol according to the Research Ramp-Up phase under which the university is operating at that time of (i.e., orange, yellow, or green).

Full participation includes 14 treatment visits and 3 follow up visits. All in-person visits will take place at Pac-TARC. In addition to testing low dose varenicline in SMI smokers for the first time, three other innovative design features are incorporated to try to improve medication tolerability and short-term quit rates. 1) Plasma will be obtained at baseline to measure participants' NMR and to identify slow versus normal nicotine metabolisers. 2) A flexible quit date (between days 8-35) will be employed allowing varenicline preloading to occur prior to the TQD. 3) Ten sessions of ACT for smoking cessation will be delivered by trained counselors first in 7 in-person sessions followed by 3 sessions delivered via telephone to all participants. Randomization of participants will occur in a 1 (low dose) to 1 (standard dose) ratio and participants will be balanced on diagnosis (BD vs SSD), gender, race (White vs. non-White) and whether or not they are taking antiepileptic medications (e.g., carbamazepine) as mood stabilizers (20) which, like the demographic/ethnic factors (11,26) can influence CYP2A6 activity and affect the NMR. Volunteered, observed and solicited NPSAEs will be assessed using standardized procedures developed in EAGLES and our other prior work (4,27). However, going beyond EAGLES, we will also assess participants' tobacco withdrawal symptoms, urges to smoke, sleep disturbances, self-efficacy & confidence to quit, and satisfaction with the protocol elements. To further extend EAGLES, we will include more "real world" participants who are somewhat less psychiatrically stable and who have comorbid substance use disorders (SUDs) in early remission.

Figure 3. Study Design – ACTSLOW Pilot Trial

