2° Efficacy Outcome: In keeping with the pilot nature of this trial, we will use 7-day point prevalence abstinence (PPA) at week 12 confirmed by expired CO levels ≥ 4 ppm and urine cotinine levels < 200 mg/ml as the secondary efficacy endpoint. We will continue to track smoking outcomes through week 24 using these same biochemical verification measures to assess 7-day PPA at week 24 as a tertiary outcome.

Other Secondary Outcome Measures: Our gathering of data on the MNWS, QSU-Brief, ISI, SEQ-12, Confidence to Quit Scale is exploratory in nature and is intended to provide preliminary information on the mechanism of action of combined varenicline and ACT in SMI smokers and their relation to NPSAEs. We will also explore ACT's effects on avoidance and inflexibility with the AIS at weeks 12 and 24.

Determination of the NMR: The ratio of trans-3'-hydroxycotinine (3HC) and cotinine (COT) will be measured in plasma using electrospray ionization liquid chromatography tandem mass spectrometry (ESI LC-MS/MS) technology adapted from the protocols described by Tanner et al. (45) and Lerman et al. (7). COT and 3HC in plasma will be determined by quantifying with standard deuterium labeled COT and 3HC, known as COT-d3 and 3HC-d3 (commercially available from Sigma-Aldrich). Plasma samples will be spiked with a known amount of COT-d3 and 3HC-d3, and samples will be subjected to MS to quantitate the endogenous levels of COT and 3HC by parallel reaction monitoring. LC-MS/MS will be performed on the high-resolution Orbitrap Q-Exactive LC -MS system located in the [name] lab in the Skaggs School of Pharmacy and Pharmaceutical Sciences. Standard plots of different amounts of deuterated and non-deuterated COT and 3HC standards into control plasma, followed by LC-MS/MS, will define the linear range of quantitative measurements, lower limit of detection, and reproducibility of replicate samples. Ratios of 3HC/COT will be calculated from quantitative MS data analyzed by the Skyline software. Reliability of these procedures in plasma is high with NMR measurements robust even to differences in analytic methods used by different laboratories (45). The NMR data will be compiled with the phenotypic data of this study to examine the relationship of NMR to NPSAEs and smoking cessation.

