To gather preliminary data on the NMR, the frequency distributions of the NMR values in this SMI sample will be compared with the published data from Lerman et al. (2015) in a large sample of NMI smokers that found a cutoff score of 0.31 as the demarcating point between slow (<0.31) and normal (including rapid) metabolisers. Based on this analysis, we will calculate Cohen's d effect sizes comparing slow metabolisers on standard dose vs. normal metabolisers on low dose, as well as standard deviations and CIs, for incidence of NPSAEs of any severity to examine the direction and magnitude of the effect. Secondary outcome measures will also be examined using the same methodologies including 7-day PPA at weeks 12 and 24, to guide future studies. Regarding the secondary efficacy outcomes, and anticipating possible quit-boosting effects from ACT and varenicline preloading, we predict 7-day PPA rates at week 12 will be at least comparable to those observed in varenicline-treated EAGLES SMI participants which was 28.2%, and that 7-day PPA rates at week 24 will be at least comparable to the 20.0% observed in EAGLES (unpublished data). To examine the possible confounding effect of variable lengths of abstinence depending on when participants first attempt to quit smoking within the quit window, we will examine the effect of a time factor (i.e., the number of days from the first dose of medication to the date of the first quit attempt) with the methodologies described above.

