Consistent with recommendations on the proper sizing for pilot studies literature (50,51,53), we chose a sample size of 60 participants based on maximal accrual expectations over a 15-month recruitment period and practical cost constraints to conduct a pilot trial in this special population of smokers. Previous studies examining target sample sizes for pilot studies have argued that as few as 12 participants per group is adequate to estimate standard deviations for a two-group study (54,55), while others have suggested that a total sample of 30 is an acceptable size for a pilot study (56). With a sample of 60 (n=30 per dosing group), we will have the ability to estimate effect sizes, standard deviations, and their CIs with adequate precision to evaluate the feasibility of study procedures and to subsequently conduct formal power analyses for future RCTs (57). As such, it is amply sized as a pilot trial. For example, given a small-to-medium estimated effect of $d=0.40$, we would have 80% confidence that the true effect fell between 0.064 and 0.733 with a pilot sample of N=60. For a smaller effect of $d=0.30$, this 80% CI becomes 0.005-0.672 providing adequate precision in detecting an effect (i.e., zero not in the CI) for use in power analyses for a larger RCT. Furthermore, applying Sims' and Lewis' (2012) calculations, the sample size of N=60 will allow us to estimate standard deviations around our feasibility estimates with a minimal inflation factor (e.g., 1.09 for one-sided 80% CIs) for use in future RCT power analyses.

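### Aim 2's only specified analysis compares two of the four NMR-by-dose cells, so it mixes NMR with dose, drops about half the participants and discards the continuous NMR

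*Combined protocol and SAP*

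**What the plan says.** Section 6 states Aim 2 as "To explore whether nicotine clearance rate as measured by the plasma" metabolite ratio influences NPSAE incidence and medication tolerability. Hypothesis 2 predicts more NPSAEs of any severity in slow metabolisers on standard dosing than in normal metabolisers on low dose.

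Section 9 (Determination of the NMR) measures the NMR as a ratio of two quantified plasma concentrations. It says the data will be used to "examine the relationship of NMR to NPSAEs and smoking cessation", but names no model.

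The Data Analytic Plan for Aim 2 says that "the frequency distributions of the NMR values in this SMI sample will be compared with the published data" from a large sample of smokers without mental illness, a study that "found a cutoff score of 0.31 as the demarcating point between slow (<0.31) and normal (including rapid) metabolisers". It continues: "Based on this analysis, we will calculate Cohen's d effect sizes comparing slow metabolisers on standard dose vs. normal metabolisers on low dose", with standard deviations and confidence intervals, for NPSAEs of any severity. Secondary outcomes, including 7-day abstinence at weeks 12 and 24, are to be examined in the same way.

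No continuous NMR term, dose-by-NMR term or summary of the other two cells is specified. The Overview in Section 9 balances randomisation on diagnosis, gender, race and antiepileptic use because these "can influence CYP2A6 activity and affect the NMR". Antiepileptic use does not appear in the Aim 2 analysis.

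**The concern.** The aim is about clearance rate, but the contrast changes two things at once: metaboliser class and varenicline dose. A difference could come from NMR, from dose, or from both. The protocol itself expects dose to matter. In its Table 2 (smokers without mental illness), insomnia is 37.2% on standard dose and 20.9% on low dose, a gap of 16.3 percentage points before NMR plays any part.

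The contrast also leaves out slow metabolisers on low dose and normal metabolisers on standard dose. Those two cells are what is needed to separate an NMR effect from a dose effect. Reducing a measured ratio to two classes loses further information.

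Aim 2 is one of only two aims, and what it delivers is an effect size for planning a larger trial. A small, confounded contrast is a poor basis for that.

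**Working it through.** **Inputs.** N = 60, 30 per arm, and d = 0.40 with an 80% CI of 0.064 to 0.733 (Section 9, Sample Size Determination). Slow share 40%: Section 7 gives "among slow metabolisers, which represents ~40% of the general population of NMI smokers". The share in smokers with serious mental illness is not given, so 20% to 60% was also run. Any-severity psychiatric event rate 36.8% (Table 1, all bipolar participants of the earlier trial), used as an assumption.

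**1. The plan's own figure.** A noncentral-t 80% interval for d = 0.40 with 30 + 30 gives 0.064 to 0.733, an exact match. The normal approximation, SE = sqrt((n1+n2)/(n1·n2) + d²/(2(n1+n2))), gives sqrt(60/900 + 0.16/120) = 0.261. The interval is 0.40 ± 1.2816 × 0.261, or 0.066 to 0.734. The approximation is therefore adequate for the comparison below.

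**2. What the contrast estimates.** Write μ for the outcome mean in each cell. Then

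μ(slow, standard) − μ(normal, low) = [μ(slow, standard) − μ(normal, standard)] + [μ(normal, standard) − μ(normal, low)].

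The first bracket is an NMR effect at standard dose. The second is a dose effect among normal metabolisers. The two cells used cannot separate them.

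**3. Precision of the contrast.** The expected slow/standard cell is 30 × 0.40 = 12 and the normal/low cell is 30 × 0.60 = 18, so 30 of 60 people are unused.

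SE = sqrt(30/216 + 0.16/60) = 0.376, and the 80% CI is 0.40 ± 0.482, or -0.08 to 0.88.

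| Comparison (d = 0.40) | n | 80% CI |
|---|---|---|
| Stated, dose arms | 30 vs 30 | 0.064 to 0.733 |
| Planned contrast, 40% slow | 12 vs 18 | -0.08 to 0.88 |
| Planned contrast, 20% slow | 6 vs 24 | -0.19 to 0.99 |
| Planned contrast, 60% slow | 18 vs 12 | -0.08 to 0.88 |
| Slow vs normal, all participants, 40% slow | 24 vs 36 | 0.06 to 0.74 |

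The half-width is 0.48 instead of 0.33. The last row shows that the widening comes almost entirely from the dropped cells.

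**4. Cost of the split itself.** For a linear effect of a normally distributed log NMR, a split at slow share p keeps φ(z_p)²/(p(1−p)) of the information. At p = 0.40 this is 0.3863²/0.24 = 0.622. It ranges from 0.490 (p = 0.20) to 0.637 (p = 0.50).

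**5. Precision of the alternative.** At a 36.8% rate, 60 people give 60 × 0.368 ≈ 22 events. Per arm, the log-odds slope per SD of log NMR has SE ≈ 1/sqrt(30 × 0.368 × 0.632) = 0.379. The interaction SE is sqrt(2) × 0.379 ≈ 0.54. A 95% CI multiplies and divides the ratio of odds ratios by about exp(1.96 × 0.535) ≈ 2.9.

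**6. Antiepileptics.** The documents give neither the share of users nor the size of the shift. Suppose a share f of users with NMR raised by s SD. The number of 60 who change class is 60 × f × (0.40 − Φ(z_0.40 − s)). With f = 0.20 and s = 0.5 this is 60 × 0.20 × (0.40 − 0.226) ≈ 2, and users are about 12% of the slow class and 24% of the normal class. Over f = 0.10 to 0.40 and s = 0.25 to 1.0 it runs from 0.6 to about 7 people.

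**The case against.** The planned contrast matches Hypothesis 2 as worded, and it sets what the protocol expects to be the worst combination against the best. The class-based approach follows the published work the protocol builds on, and if the true effect is closer to a threshold, the 62% figure does not apply. Aim 2 is declared exploratory and the trial is not powered for clinical outcomes. The proposed interaction is itself imprecise. All of this stands. It bears on how much the point matters, and it is a reason to keep the hypothesised contrast on display. It does not make that contrast answer the aim's question about clearance rate.

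Antiepileptic use is also not ignored: randomisation is balanced on it. That protects the comparison of dose arms. It does not protect a comparison of NMR classes, which are not randomised, or the comparison with the published sample. On the other hand, if these drugs truly change CYP2A6 activity, a shifted NMR may reflect real clearance and not error. That argues for description and a sensitivity analysis, not for excluding users.

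A reader might infer from the order of the text (distribution first, then effect sizes) that the cutoff will be chosen from the data and that this would overstate the effect. The documents do not support that. They name one cutoff and no rule for deriving another, and a cut set from the NMR distribution without sight of outcomes does not by itself inflate the effect. In a null simulation, picking the most favourable of five cuts on the outcome raised the share of 80% intervals wholly above zero from 10.6% to 17.7%, but the plan describes no such selection. What is missing is only a statement that 0.31 is fixed.

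**Conclusion.** The point holds for the two-cell contrast. It confounds NMR class with dose whatever the data show, and that conclusion needs no assumption. At a 40% slow share it rests on about 12 versus 18 people, with an 80% CI half-width of 0.48 where the quoted precision implies 0.33. The Sample Size section's figures therefore do not describe Aim 2. The share is borrowed from smokers without mental illness; at 20% slow the interval is wider still.

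The loss from splitting NMR (about 62% of the information kept) is a separate matter and depends on a linear effect and a normal log NMR. It is tempting to multiply 60 by 0.622 and say that the plan is like analysing 37 people. That does not follow, because the 62% refers to slow versus normal in all 60, which is not the comparison planned.

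The unlocked cutoff and the absence of antiepileptic use from the analysis are gaps in detail. The size of any antiepileptic effect cannot be derived from the documents. Because Aim 2 is exploratory, precision and interpretability are at stake, not error control. This is a worthwhile, inexpensive improvement and not a flaw in the trial's validity.

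**What to change.** Before NMR is linked to outcomes, amend the Aim 2 text as follows.

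- **Main exploratory estimate:** logistic regression of any-severity NPSAEs on continuous log NMR, dose and their interaction, in all randomised participants with an NMR value, reported with confidence intervals. Use penalised logistic regression if events are sparse. Report how many lack an NMR value, since Red-phase baselines collect no blood.
- **Display:** keep slow/normal at 0.31, stated as fixed in advance. Show all four NMR-by-dose cells with counts and events, including the hypothesised contrast.
- **Antiepileptics:** show the NMR distribution and slow share by antiepileptic use, and add use as a covariate in a sensitivity analysis.
- **Precision:** state that the quoted 30-versus-30 interval does not apply to the Aim 2 contrast.

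The cost is SAP wording and one model, with no new data: the NMR is already planned and antiepileptic use is already recorded for randomisation. The downsides are a linearity assumption, which a plot can check, and an imprecise interaction (SE about 0.54 on the log-odds scale per SD of log NMR if the 36.8% rate applies, and larger if NMR values are missing). The report should say so.

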Would Lower Dosages of Varenicline Be Better Tolerated, Especially Among Slow Metabolisers? It is also important to determine whether a lower dose of varenicline can be used in some smokers to reduce medication side effects without significantly reducing efficacy. Our earliest work with the medication in a Phase II trial in NMI smokers found that 0.5 mg twice daily titrated varenicline - - one-half of what eventually became the FDA-approved titrated dose of 1 mg twice daily, produced similar quit rates to the approved dose (13), a result confirmed in a related Phase II varenicline trial (14) and a recent Phase IV trial (15). However, all of these studies also found lower rates of treatment emergent AEs in the lower dose varenicline group. While **none of the earlier studies focused on NPSAEs**, in the Oncken et al. trial (2006) discontinuation rates due to AEs and the incidence of nausea, insomnia, and abnormal dreams were markedly lower among low-dose treated participants compared with standard-dose treated smokers (13; see Table 2). Reducing NPSAEs in SMI smokers is particularly salient because, as we have shown in the EAGLES trial (see Figure 2), BD and SSD smokers are 3- to 5-times more likely than NMI smokers to experience moderate to severe NPSAEs when trying to quit using 1st-line medications or placebo. Moreover, although at times difficult to disentangle from negative affective symptoms associated with nicotine withdrawal, our more recent analysis of NPSAEs of any intensity level in BD smokers reveals a 61% increase among varenicline-treated participants compared with placebo (see Table 1), begging the question whether lower doses might help reduce the incidence of NPSAEs.

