Regardless of Treatment, SMI Smokers Were 3- to 5-Times More Likely to Experience Clinically Significant NPSAEs than NMI Smokers: Using a composite primary neuropsychiatric safety endpoint developed in consultation with the U.S. FDA4, we found the risk for moderate to severe NPSAEs was significantly higher in SSD smokers (Risk Difference [RD]% = 3.96; 95% CI = 1.63 – 6.29) and BD smokers (RD% = 7.73; 95% CI = 4.15 – 11.3) compared with NMI smokers. The observed incidence of the primary composite NPSAE endpoint for the two groups is depicted below (see Figures 2a and 2b). Although there was no evidence for a significant risk difference by treatment in the BD subcohort, the observed incidence of clinically significant NPSAEs was highest among varenicline-treated participants.

Figure 2. Incidence of Moderate-to-Severe NPSAEs in BD vs NPC Smokers & SSD vs. NPC Smokers

Rates of NPSAEs of Any Severity Were Higher Among Varenicline BD Smokers Compared with Placebo BD Smokers: In contrast to the pre-specified primary composite safety endpoint that was designed to capture clinically significant, moderate to severe NPSAEs, Table 1 below illustrates the rates of NPSAEs reported at $\geq 1\%$ at any severity level (mild, moderate or severe) and coded according to the MedDRA category psychiatric disorders. Compared with placebo, varenicline-treated BD smokers had significantly higher rates of NPSAEs of any intensity, including sleep disorders.

Table 1. Neuropsychiatric Adverse Events of Any Severity in EAGLES Bipolar Participants

Mild, Moderate or Severe AEs* Coding to the MedDRA Category Psychiatric Disorders	All BD Subjects	Varenicline	Bupropion	NRT	Placebo
Any Psychiatric AEs	36.8%	45.3%	44.0%	25.0%	28.1%
Depressed mood disorders and disturbances	11.1%	16.0%	13.1%	4.7%	8.8%
Manic and bipolar mood disorders and disturbances	5.0%	6.7%	7.1%	0%	5.3%
Sleep Disorders & Disturbances	18.2%	26.7%	19.0%	14.1%	10.5%

AE = adverse event; BD = bipolar disorder; NRT = nicotine replacement therapy (transdermal nicotine patch)

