Sample Size Determination: The aims of this pilot trial are to gather preliminary data or demonstrate proof of principle with potential for high impact within one or more stated research priorities of the funding agency. Thus, Aim 1 of the proposal addresses feasibility while Aim 2 is exploratory and begins to test the principle as to whether NMR influences NPSAE propensity and medication tolerability in SMI smokers by estimating effect sizes. The study is designed to provide preliminary data on the feasibility of a larger RCT that would further develop these novel pharmacotherapy approaches in SMI smokers. It is not powered to test clinical outcomes, thus, safety (incidence of NPSAEs) and efficacy (7-day PPA at week 12 and at week 24) outcome measures are considered secondary endpoints. In our group's previous work with varenicline in EAGLES (4) and another trial done in SMI smokers (49), we randomized ~80% of those screened and retained >80% of study participants. Similar retention rates were found in another pilot trial of varenicline in bipolar smokers (52) and in [name] preliminary study. Therefore, we expect that with N=60 we will be able to adequately determine the feasibility of the proposed study procedures.

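### The only effect size specified for Aim 2 changes nicotine metabolite ratio (NMR) and dose together, so it cannot show whether NMR influences neuropsychiatric adverse events

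*Combined protocol and SAP*

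**What the plan says.** Section 6 states Aim 2 as exploring whether "NMR influences the incidence of NPSAEs and medication tolerability in varenicline-treated SMI smokers". The Sample Size Determination in section 9 says that Aim 2 "begins to test the principle as to whether NMR influences NPSAE propensity and medication tolerability in SMI smokers by estimating effect sizes".

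Hypothesis 2 and the Aim 2 analysis are narrower. Using an NMR cutoff of 0.31, the Data Analytic Plan gives one effect size for NPSAEs of any severity: Cohen's d "comparing slow metabolisers on standard dose vs. normal metabolisers on low dose", with standard deviations and confidence intervals, to show direction and magnitude.

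Two other statements bear on the point:

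- Determination of the NMR (section 9) says NMR data will be combined with the other study data "to examine the relationship of NMR to NPSAEs and smoking cessation". It names no contrast or model.
- For the remaining outcomes, "Secondary outcome measures will also be examined using the same methodologies including 7-day PPA at weeks 12 and 24". This could mean the same two groups or only the same statistics.

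No comparison of slow with normal metabolisers at the same dose is written out, and neither is a dose-adjusted NMR effect or an NMR-by-dose interaction. The Medication Tolerability measures are reported by dosing arm, without reference to NMR.

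**The concern.** NMR group and dose arm define four cells. The specified contrast takes one diagonal: slow/standard against normal/low. Moving from one cell to the other changes both factors, so the expected difference is the NMR effect plus the dose effect. No sample size separates them.

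A dose effect is a live alternative, because the trial is built around it. Section 7 notes a higher NPSAE rate on varenicline than on placebo in bipolar smokers, "begging the question whether lower doses might help reduce the incidence of NPSAEs". If lower dosing does reduce these events and NMR does nothing, the contrast still tends to favour Hypothesis 2. It could then be read as evidence on NMR and carried into the larger trial that this pilot is meant to inform.

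**Working it through.** **Inputs**

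- 60 participants, 30 per dose arm, randomised 1:1 (section 9).
- About 40% slow metabolisers (section 7). This figure is for smokers without mental illness and is an assumption here; 25% to 50% is shown.
- Any psychiatric adverse event in bipolar smokers in the earlier trial: 45.3% on standard-dose varenicline, 28.1% on placebo; sleep disorders 26.7% on varenicline (Table 1).
- Low-dose reductions in smokers without mental illness: abnormal dreams 40%, discontinuation due to adverse events 35% (Table 2).

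**1. Identification.** For illustration, let the low dose remove half of the excess over placebo: (45.3 - 28.1)/2 = 8.6 points, so 45.3 - 8.6 = 36.7%. All four scenarios below give the same diagonal difference, 45.3 - 36.7 = 8.6.

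| Scenario | Slow/standard | Normal/standard | Slow/low | Normal/low | Slow minus normal, within each dose |
|---|---|---|---|---|---|
| Dose only | 45.3 | 45.3 | 36.7 | 36.7 | 0 |
| NMR only | 45.3 | 36.7 | 45.3 | 36.7 | +8.6 |
| Half of each | 45.3 | 41.0 | 41.0 | 36.7 | +4.3 |
| Reversed NMR, dose effect 17.2 | 45.3 | 53.9 | 28.1 | 36.7 | -8.6 |

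The planned statistic cannot tell these apart. The argument does not depend on the rates chosen.

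**2. Precision.** The plan states that for d=0.40 "we would have 80% confidence that the true effect fell between 0.064 and 0.733 with a pilot sample of N=60". A noncentral-t 80% interval with 30 vs 30 gives 0.064 to 0.733, so the figure reproduces. It is a comparison of whole dose arms. The Aim 2 contrast has about 30 × 0.40 = 12 slow on standard dose and 30 × 0.60 = 18 normal on low dose:

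| Share slow | Expected groups | 80% CI at d=0.40 |
|---|---|---|
| 25% | 7.5 vs 22.5 | -0.15 to 0.94 |
| 40% | 12 vs 18 | -0.09 to 0.88 |
| 50% | 15 vs 15 | -0.08 to 0.87 |

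Numbers would be lower still if NMR is missing, for example for participants randomised in the Red Phase, when no blood is drawn.

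**3. How often a dose effect alone points the expected way.** Assume no NMR effect, 45.3% on standard dose, and 12 vs 18. The exact binomial probability that the slow/standard proportion exceeds the normal/low proportion is:

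| Assumed dose effect (points) | Low-dose rate | P(difference > 0) |
|---|---|---|
| 0 | 45.3% | 0.469 |
| 8.6 (half the excess over placebo) | 36.7% | 0.652 |
| 0.40 × 26.7 = 10.7 | 34.6% | 0.694 |
| 0.35 × 45.3 = 15.9 | 29.4% | 0.789 |

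All three reduced rates stay above the 28.1% placebo rate. Over every split from 8 vs 22 to 15 vs 15 the four probabilities range over 0.43-0.50, 0.62-0.68, 0.66-0.72 and 0.76-0.81.

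**4. A contrast that targets NMR.** Take slow minus normal within each dose arm and average the two. At 45.3% and 36.7%, with 12 slow and 18 normal per arm:

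- Pooled: variance = (0.453×0.547 + 0.367×0.633) × (1/12 + 1/18) / 4 = 0.0167; SE = 0.129; 80% half-width = 1.2816 × 0.129 = 16.5 points (18.7 at 25% slow, 16.2 at 50%).
- Diagonal: variance = 0.453×0.547/12 + 0.367×0.633/18 = 0.0336; SE = 0.183; 80% half-width = 23.5 points.

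The pooled estimate uses everyone with an NMR value. The NMR-by-dose interaction has SE = sqrt(2 × (1/12 + 1/18)) = 0.53 SD, so it can only be descriptive.

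**The case against.** The strongest reply is that the analysis does what Hypothesis 2 says, and that Aim 2 is exploratory, with no formal testing and NPSAEs as a secondary endpoint. The match is real, but Hypothesis 2 as worded can be true when NMR has no effect, so confirming it does not answer Aim 2. The exploratory status excuses wide intervals; it does not make a joint difference into an NMR effect.

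Several further points stand, without removing the problem:

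- The confounding is in this contrast, not the design. Dose is randomised and NMR is measured before treatment, so all four cells should be available.
- The quoted interval is given for dosing groups and is not claimed for Aim 2. But no other precision figure is offered for effect sizes, and 12 vs 18 is within the pilot sizes the plan cites.
- The dose effects in step 3 are borrowed. The 35% concerns discontinuations and the 40% abnormal dreams, both in smokers without mental illness. The reversed-NMR scenario runs against section 7, which reports slow metabolisers as more prone to side effects. These are illustrations only.
- The sign of a point estimate is weak evidence, and the plan will report intervals.
- The pooled contrast is itself imprecise, averages over any interaction, and compares groups that were not randomised.

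**Conclusion.** The concern holds. The only effect size specified for Aim 2 estimates the NMR and dose effects together, and the data it uses cannot give the size or even the sign of the NMR effect. An 8.6-point difference is compatible with a within-dose NMR effect of 0, +4.3, +8.6 or -8.6 points. This conclusion needs no assumption about event rates.

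The loss of precision is secondary: about 30 of 60 participants are used, and the 80% CI at d=0.40 widens to -0.09 to 0.88 if 40% are slow. The sign probabilities of 65% to 79% under a pure dose effect, against 47% with no effect, rest on a bipolar-only event rate and borrowed dose reductions.

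This should be fixed before analysis. It does not threaten the feasibility aim or the conduct of the trial.

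**What to change.** In the Aim 2 analysis plan:

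1. Make the main estimate slow vs normal within each dose arm, pooled across arms (for example a Mantel-Haenszel risk difference, or a model with NMR group and dose), in all randomised participants with an NMR value. State how many lack one.
2. Keep the slow/standard vs normal/low contrast as descriptive, labelled as a joint NMR-plus-dose difference, and word Hypothesis 2 to match.
3. Report low vs standard dose overall and within each NMR group.
4. State the same contrasts for 7-day abstinence at weeks 12 and 24.
5. Give confidence intervals throughout, label everything exploratory, and describe NMR results as associations.

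The NMR-by-dose interaction, NMR on a continuous log scale, and adjustment for factors that affect NMR are optional additions.

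The cost is SAP wording and a few more exploratory estimates, with no new data or participants. The pooled estimate stays imprecise (80% half-width about 16 to 19 points for 50% to 25% slow), but it addresses the question the aim asks and is tighter than the diagonal contrast.
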